4 TREATMENT PLAN

4.1 DEFINITION OF STUDY STAFF

4.1.1 AT THE STUDY SITE

At each study center the staff will consist of a minimum of two neurologists. One neurologist will be the Treating Neurologist and one will be the Examining Neurologist for a given subject throughout the study. An MRI radiologist and technologist, and a clinical coordinator, and a pharmacist (or another authorized staff member) must also be members of the study staff at each center. A technician/staff nurse qualified to perform MSQoL54 (inclusive of SF36) and FIS must also be a member of the study staff at each center. When performing a relapse assessment or disability progression, the results from the Treating and Examining Neurologist will not be shared.

4.1.2 PRINCIPAL INVESTIGATOR

At each investigational center, a neurologist will be appointed to serve as a Principal Investigator and will have overall responsibility to lead the site study team (neurologists, radiologists, technicians, staff nurses, pharmacists and clinical coordinators) in all aspects of the study. The Principal Investigator will oversee the recruitment and accrual of appropriate subjects, the conduct of the study according to the study protocol, and the collection of required study data and regulatory requirements including timely reporting of all SAEs. The Principal Investigator may be the Treating Neurologist for a given subject but cannot be the Examining Neurologist (see Sections 4.1.3 and 4.1.4 for the roles and responsibilities of the Treating Neurologist and Examining Neurologist, respectively).

4.1.3 TREATING NEUROLOGIST

The Treating Neurologist will be responsible for subjects' care, eligibility evaluation, supervision of study medication administration, recording and treating of adverse events, serious adverse events and assessing and treating of MS relapses, performing neurological examinations and monitoring of safety assessments, including routine laboratory results and concomitant medications. The Treating Neurologist will provide no information to the Examining Neurologist. The MSFC and SDMT assessments may be performed by the Treating Neurologist, or may be delegated to another qualified team member, but must not be performed by the Examining Neurologist. The Treating Neurologist (who does not perform the EDSS assessment), other investigative site staff and subject should not have access to Examining Neurologist's EDSS scores. It is encouraged that the same physician maintain the role of Treating Neurologist for a given subject throughout the study.

4.1.4 EXAMINING NEUROLOGIST (EVALUATING NEUROLOGIST)

The Examining Neurologist (EDSS Rater) will be responsible for conducting and documenting all EDSS assessments. The Examining Neurologist will not share the findings of the EDSS assessment when evaluating relapses with the Treating Neurologist. The Examining Neurologist must possess current EDSS rater certification (Level C). Throughout the study, the Examining Neurologist is blinded to all subject information collected by the Treating Neurologist which includes adverse events, concomitant medications, laboratory results, and any clinical MS examination for enrolled subjects. Additionally, the Examining Neurologist should not have access to any prior EDSS scores from any time throughout the study or any clinical information when performing their examination.

The Examining Neurologist will also be responsible for entering the EDSS assessment data into the electronic Case Report Form (eCRF). The entry of EDSS assessment data into eCRF may be delegated to another staff member, provided that the staff member has been trained in the eCRF, maintains the same level of blinding as that of the Examining Neurologist and is not involved in any other study-related activities, other than EDSS assessments.

Every effort should be made to ensure that there is no change in the EDSS Rater throughout the course of the study for any individual subject. Whenever possible, the same person should perform the examination for the full study duration. All members of the study staff at the clinical site and the subject should not discuss safety issues with the Examining Neurologist. Subjects will be instructed not to discuss any clinical symptoms or experiences while on trial with the Examining Neurologist. The Examining Neurologist should remind the subject at the start of the examination to not discuss any clinical symptoms or experiences while on trial.

In exceptional cases, where a site clinical research nurse or a clinical coordinator has neurostatus EDSS rater certification level C and extensive experience with EDSS assessments in clinical trials, they may be delegated the responsibilities of the Examining Neurologist provided the required level of blinding is maintained. Additionally, TG Therapeutics' written approval will be required in advance of such a delegation.

The Treating Neurologist and the Examining Neurologist will NOT be allowed to switch roles.

4.1.5 MRI STAFF

The MRI staff will be responsible for performing the MRI according to the protocol and MRI manual. They will also prepare adequate electronic material according to the MRI manual for transfer of images to the central MRI reader. The MRI manual will provide instructions for storage of the primary data at the site.

Radiologist will review MRI scans locally for non-MS pathology and will provide reports to the Treating Neurologist. Local MRI reports after randomization must not contain details of the MS pathology, MRI scans will be read centrally for MS pathology by the central MRI reader.

4.1.6 CLINICAL COORDINATOR

The clinical coordinator will be responsible for coordinating and assisting all study site staff, including subject scheduling and completion and monitoring of all subjects' electronic Case Report Forms. He/she will instruct the subjects on proper study medication administration, subject diary adherence, obtain vital signs, collect, process, and send all blood and urine samples and requests to the central laboratory. Additionally, he/she will be responsible for administering the subject-reported questionnaires (MSQoL-54 and FIS) and coordinating subject's appointment with other departments, e.g., imaging facility etc. Some or all of these study-related activities may instead be performed by the Treating Neurologist or a qualified technician/staff nurse.

4.2 STUDY COMMITTEES

4.2.1 DATA SAFETY MONITORING BOARD (DSMB)

The DSMB will be an independent group of individuals not involved in the study or study sites or have other conflicts of interest with the study and are charged with reviewing safety data and conduct of the trial. The independent DSMB will be comprised of five members with at least three MDs, a biostatistician, and the DSMB chair. The responsibilities of the DSMB will be described in a DSMB Charter. The committee will meet periodically, but at least annually to fulfill the duties and obligations outlined in the DSMB Charter. Minutes of these meetings will be prepared as specified in the DSMB Charter. There will be minutes from both an open session which will be transmitted to the Sponsor and CRO and minutes of the closed session maintained by an unblinded DSMB Coordinator from CRO until the study is complete, at which point they will be transmitted to the Sponsor and CRO. Statistical analyses required for the planned DSMB meetings will be prepared and disseminated to the DSMB members. The committee will receive unblinded safety data to allow review and assessment by treatment group. In addition, the committee will receive unblinded efficacy data to perform benefit/risk ratio assessment. On the basis of their reviews and analyses of safety and efficacy data, the committee shall have the right to advise the sponsor to stop the study after any meeting for efficacy or detrimental effects or futility. The process and options will be specified in the Charter.

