4.3.1 STOPPING RULES

There are no pre-planned interim analyses planned with formal stopping rules for effectiveness. The DSMB may make recommendations to stop the trial and will provide their rationale justification along with such a recommendation as will be specified in the DSMB Charter.

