The purpose of this follow-up is to monitor safety and relapses after the discontinuation of study medications and to eliminate residual teriflunomide from the study subjects. Because blinding is maintained until the data from the treatment period (through Week 96) is locked, all subjects will undergo the accelerated teriflunomide elimination procedure regardless of whether they were randomized to ublituximab/oral placebo or teriflunomide/IV placebo. Study subjects that enter the Follow-up Period of TG1101-RMS302 (post-Week 96 to Week 116) are not allowed to receive DMTs. Please refer to the exclusion criteria of the protocol for a list of MS therapies (Section 3.2). It should be noted that use of systemic corticosteroids for the treatment of a relapse is allowed. When deciding

TG1101-RMS302

Dated: 04 September 2020 (Ver. 5.0)

Page 66 of 140

to treat a potential acute relapse the Treating Neurologist can use IVMP (1.0 g/day for at least 3 days and can be extended to 5 days).

The procedures of each visit are below:

Week 100 Visit:

- Physical examination and vital signs
- Urine pregnancy test
- Report concomitant medications and Adverse Events
- Initiate rapid teriflunomide elimination program (Section 6.10.1 below)
- Hematology and serum chemistry, urinalysis, and B cell assays (as per Section 6)

Week 104 Visit:

- Physical examination and vital signs
- Urine pregnancy test
- Report concomitant medications and Adverse Events
- Hematology and serum chemistry, urinalysis, and B cell assays (as per Section 6)
- Acknowledgment of the completion of teriflunomide rapid elimination program by the site on eCRF

Week 108 and 112 (Phone Call):

- Follow-up phone call to subject to collect information on concomitant medications, Adverse Events and urine pregnancy test outcomes

Week 116 Visit (Final Visit):

- Physical examination and vital signs
- Urine pregnancy test
- Report concomitant medications and Adverse Events
- Teriflunomide drug concentration test: Draw blood to test teriflunomide plasma concentration

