8 STATISTICAL CONSIDERATIONS

This section describes the statistical methods to be used to analyze the efficacy and safety endpoints. Safety related analyses are described in Section 9. Full details will be provided in a formal statistical analysis plan (SAP). The final Clinical Study Report will describe deviations from the SAP, if any.

The statistical analyses will be done once all subjects have completed Week 96 (Week 96 visit or earlier if withdrawn).

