### 3 Interim Analysis

There are no interim efficacy analyses planned for this study.

A preplanned interim analysis for sample size reassessment will be performed by BART.

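### Protocol 4.2.1 lets the DSMB advise stopping for efficacy after any meeting, which contradicts SAP 3, the single Week 96 analysis at full alpha, and Protocol section 10

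*Protocol*

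**What the plan says.** Protocol section 4.2.1 states that "the committee will receive unblinded efficacy data to perform benefit/risk ratio assessment", and then that "the committee shall have the right to advise the sponsor to stop the study after any meeting for efficacy or detrimental effects or futility". The board meets at least annually; no maximum is given. The section ends by deferring detail: "The process and options will be specified in the Charter".

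Elsewhere the plan describes one efficacy analysis at the end:

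- SAP section 3: "There are no interim efficacy analyses planned for this study". The only interim analysis it foresees is the sample size reassessment by the blinded relapse team.
- Protocol section 8 and SAP section 2.4 both time the statistical analyses to when all subjects have completed Week 96 or withdrawn.
- Protocol sections 8.2 and 8.9 give the primary test the whole two-sided 0.05.
- Protocol section 10, headed Stopping Rules, mentions only safety as a reason for the DSMB to stop the study.
- The synopsis (Study Design) repeats the DSMB's right to advise stopping after any meeting but does not name efficacy as a ground.
- Protocol section 4.3.1: "There are no pre-planned interim analyses planned with formal stopping rules for effectiveness". It adds that the DSMB may recommend stopping and "will provide their rationale justification along with such a recommendation as will be specified in the DSMB Charter".

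**The concern.** A trial that can be stopped for efficacy on unblinded data at repeated meetings needs a rule for how strong the evidence must be and how the error rate is shared with the final test. Neither the protocol nor the SAP, as far as they can be read, gives such a rule, and the SAP says that no such analysis exists. If the sponsor acted on an efficacy recommendation and claimed success, nothing in these two documents would show that the primary claim kept its 5%.

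A second consequence does not depend on alpha. All six key secondary endpoints in Protocol section 8.9.2 are defined by, during or up to Week 96. A stop at a year-1 or year-2 meeting would come before most or all subjects had reached that horizon.

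**Working it through.** **The plan's own figure.** One two-sided test at |Z| > 1.960 gives 2 × (1 − Φ(1.960)) = 0.0500. The stated 5% is right for a single Week 96 analysis.

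**Inputs from the documents.** Enrolment takes 6 to 10 months (synopsis, Estimated Study Duration). Treatment lasts 96 weeks, which is 672/365.25 = 1.840 years. The DSMB meets at least annually (4.2.1).

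**Assumptions, which are not in the plan.** Enrolment is uniform over A years and there is no dropout. Information is proportional to person-years. Meetings fall at calendar years 1 and 2, and the final analysis at the last subject's Week 96 (A + 1.84, or 2.34 to 2.67 years). Each look tests the primary statistic at nominal 1.96.

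**Information fractions.** At year 1 nobody has reached the 1.840-year cap, so the fraction is (1 − A/2)/1.840. At year 2 only those enrolled in the first 2 − 1.840 = 0.160 years are complete, so the fraction is 1 − (A − 0.160)²/(2A × 1.840).

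- A = 0.5: 0.75/1.840 = 0.408; 1 − 0.340²/(1.0 × 1.840) = 0.937.
- A = 0.75: 0.625/1.840 = 0.340; 1 − 0.590²/(1.5 × 1.840) = 0.874.
- A = 0.833: 0.583/1.840 = 0.317; 1 − 0.673²/(1.667 × 1.840) = 0.852.

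**Overall error.** Under the null, the Z statistics at looks j < k have correlation √(Iⱼ/Iₖ). The chance of crossing 1.96 at any look, from multivariate normal integration and confirmed by simulation, is:

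| Enrolment | Fractions | Two-sided | Favouring ublituximab |
|---|---|---|---|
| 6 months | 0.408, 0.937, 1 | 0.0952 | 0.0476 |
| 9 months | 0.340, 0.874, 1 | 0.1012 | 0.0506 |
| 10 months | 0.317, 0.852, 1 | 0.1030 | 0.0515 |

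The single-analysis values are 0.05 and 0.025. With only the year-1 look plus the final, the error favouring ublituximab is 0.0430 to 0.0444; with only the year-2 look plus the final, 0.0308 to 0.0340. Six-monthly meetings, which the protocol's wording allows, would take the two-sided error to about 14 to 16%.

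**Share of subjects past Week 96.** This is max(0, (t − 1.840)/A). At year 1 it is 0 for every A. At year 2 it is 0.160/0.5 = 32%, 0.160/0.75 = 21% and 0.160/0.833 = 19%.

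**The case against.** The strongest reply is that the board only advises, that it receives efficacy data to weigh benefit against risk, and that no document prescribes a significance test at its meetings. Benefit/risk review spends no alpha. That stands, and it limits the point: the 9.5 to 10.3% belongs to a procedure the plan does not contain. A reader might infer that this trial's type I error is about 10%. The documents do not support that.

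The second reply is that both 4.2.1 and 4.3.1 refer to a DSMB Charter, which may hold a boundary. This also stands, and parts of the statistical text are redacted, so the absence of a boundary is judged on readable text. It does not remove the contradiction: with a boundary only in the Charter, the SAP would still deny any interim efficacy analysis and the final test would still use the full 0.05.

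Third, a reader might take 4.3.1 as flatly contradicting 4.2.1. It does not. It denies only pre-planned analyses with formal effectiveness rules and itself allows reasoned recommendations to stop. The two sections can be read together as discretionary advice without a formal rule. The direct conflicts are with SAP 3, the Week 96 timing at full alpha, and section 10.

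Two other passages might seem to add weight but do not. The sentence in Protocol section 6.10 about keeping the blind until the Week 96 data are locked explains why every subject undergoes teriflunomide elimination; the DSMB is unblinded by design. The synopsis lists relapses for DSMB review without saying that they are adjudicated, but that is shorthand in a list and shows no defect.

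**Conclusion.** The protocol and SAP are inconsistent as written, whatever the Charter says. One sentence in 4.2.1 grants advice to stop for efficacy at an uncapped number of meetings, while the rest of the plan allows for a single efficacy test and reserves no alpha for anything earlier. The inconsistency is certain. Harm to the error rate is contingent: it requires that meetings act as unadjusted efficacy tests, that the sponsor stops on the advice, and that it then claims success. Under those conditions with annual looks, two-sided error would be about 9.5 to 10.3% instead of 5%, and the chance of a false claim for ublituximab would roughly double from 2.5% to about 5%. This should be corrected because it touches the confirmatory claim and the correction is small.

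**What to change.** Delete the words *efficacy or* from the stopping sentence in Protocol section 4.2.1. State there and in the synopsis that the DSMB reviews efficacy data for benefit/risk only and that no efficacy claim is made before the Week 96 analysis. Reconcile section 10 with 4.2.1 on the grounds for a DSMB recommendation, since 4.2.1 would still list futility and section 10 does not. The cost is a few lines of text and the loss of a discretionary efficacy recommendation. Sample size and data collection do not change.

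If the sponsor wants to keep an efficacy stop, the protocol, SAP and Charter must either fix the number of looks or adopt an alpha-spending function, with a final critical value that holds 5% overall. Protocol sections 4.3.1 and 10 and SAP section 3 must then be amended. As an illustration with annual looks and 9 months' enrolment, O'Brien-Fleming-type spending gives nominal two-sided levels of about 0.0002, 0.033 and 0.041. Requiring p < 0.001 at interims while leaving the final test at 0.05 is close but does not hold 5%: overall error is about 5.04 to 5.05% with annual looks, about 5.1% with six-monthly looks and about 5.2 to 5.3% with quarterly looks.

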4.2.2 STEERING COMMITTEE

An external Steering Committee will provide general guidance, assist with liaison to investigators and oversee some external communication of the results of the study.

4.2.3 INDEPENDENT RELAPSE ADJUDICATION PANEL (IRAP)

The IRAP will make all protocol-defined relapse determinations in this study. The IRAP will review all subject-reported, suspected, on-study relapses (i.e., new or worsening neurological symptoms) and all potential events are sent to the IRAP regardless of whether the Treating Neurologist considered the subject's symptoms to be the result of a relapse. Please see Appendix D, and Section 6.3.1 of this protocol, and the IRAP Charter for further details.

4.2.4 BLINDED ASSESSMENT RELAPSE TEAM (BART)

An independent committee, Blinded Assessment Relapse Team (BART), reporting to TG Therapeutics, and the DSMB will reassess the sample size for the study when 210 of the 220 participants in each arm have been randomized. Team will consist of a chair, 1 biostatistician and 1 other neurologist with MS experience.

4.3 DOSING SCHEMA

Table 3: Ublituximab/Oral Placebo and Teriflunomide (14 mg)/IV Placebo

	Week 1 Day 1	Week 3 Day 15	Week 24	Week 48	Week 72	Week 96
Ublituximab plus oral placebo	UTX (150 mg/ 4h)	UTX (450 mg/ 1h)	UTX (450 mg/1h)	UTX (450 mg/ 1h)	UTX (450 mg/ 1h)	
	Oral Placebo QD* from Week 1 Day 1 until the last day of Week 95					
Teriflunomide plus placebo infusion	Teriflunomide (14 mg) QD* from Week 1 Day 1 until the last day of Week 95					
	Infusion Placebo	Infusion Placebo	Infusion Placebo	Infusion Placebo	Infusion Placebo	

*May be taken in the morning daily. Alternative dosing times are allowed if necessary.

4.3.1 STOPPING RULES

There are no pre-planned interim analyses planned with formal stopping rules for effectiveness. The DSMB may make recommendations to stop the trial and will provide their rationale justification along with such a recommendation as will be specified in the DSMB Charter.

4.4 GENERAL CONCOMITANT MEDICATION AND SUPPORTIVE CARE GUIDELINES

The following treatments are prohibited while on clinical trial: other investigational drug treatments or interventional study participation, other DMTs used to treat MS, radiation therapy, hormonal therapy for cancer, cancer immunotherapy or other biologic therapy excluding study medication. The exceptions to this are:

- No glucocorticoids may be administered outside of protocol requirements for pre-medication or AE management, except low doses of steroids stabilized at ≤ 10 mg per day of prednisone or equivalent, and started at least 7 days prior to study entry (Screening).

Antiemetic for Ublituximab or IV placebo: Ublituximab or IV placebo is considered to be of low emetogenic potential that may be adequately prevented with prochlorperazine. Other antiemetic may be used at the discretion of the Treating Neurologist/PI if nausea and/or vomiting is not adequately controlled/prevented.

Pre-medication prior to infusion with ublituximab or IV placebo: Infusion Related Reactions have been reported with ublituximab or IV placebo with more profound reactions in subjects with hematologic malignancies. All subjects treated with ublituximab or IV placebo require pre-medication 30–60 minutes prior to each dose of ublituximab or IV placebo with an antihistamine (diphenhydramine 50 mg or equivalent; administered orally), and a corticosteroid (dexamethasone 10-20 mg or equivalent; administered orally).

Treatment of IRR: Symptomatic infusion reactions despite pre-medication, may be treated at the discretion of the treating physician, including but not limited to: oral acetaminophen 650 mg (only used for intervention), corticosteroids, antihistamines, oxygen and bronchodilators.

Note: In case the above referenced medications are not available, equivalents can be used at the investigator's discretion. If medications are given intravenously, the IV line used for ublituximab/IV placebo should not be used. If needed, please consult the Medical Monitor.

Antihypertensive Medications: Since infusion related hypotension may occur, the investigator should carefully consider withholding anti-hypertensive medication during the 24 hours prior to, and throughout the IV infusion of ublituximab or placebo.

4.4.1 MS RELAPSE DURING THE STUDY

MS Relapses During the Study

Subjects enrolled into the study will be closely monitored through the study course by the Site and Sponsor's personnel as well as by an external independent Data Safety Monitoring Board (DSMB) to ensure subjects' welfare.

Relapses that occur after study drugs are withdrawn will be assessed over the remainder of the study period and this data will be utilized as part of additional sensitivity analysis (described in the statistical plan) as long as the subject has not withdrawn their consent to be in the trial.

The confirmation of a protocol-defined relapse will be determined by the Independent Relapse Adjudication Committee (IRAP). The steps for confirming a relapse are as follows:

1. Subject Reported Relapse

Subjects who experience new or worsening neurologic symptoms are instructed to contact the Treating Neurologist within 48 hours of symptom onset. All new or worsening neurological events, reported at a visit or over the phone, consistent with MS representing a clinical relapse as assessed by the subject will be initially reported to the Treating Neurologist. In parallel, the Examining Neurologist will also be notified to perform additional assessments. Upon the notification to the Treating Neurologist, the time and date of suspected subject reported relapse will be documented in the dedicated page eCRF (subject reported) by the Treating Neurologist or designee.

The following should be recorded in the eCRF (subject reported) by the Treating Neurologist or designee:

- Date and time of symptom onset as reported by the subject
- Symptoms and events reported by the subject (both neurological and non-neurological)
- Date of initial contact by subject
- Time of initial contact by subject

Within 7 days of the subject reporting the suspected relapse to the Treating Neurologist, the subject will be scheduled and assessed by both the Treating and Examining Neurologist independently.

2. Initial Assessment of Relapse by Treating Neurologist and Examining Neurologist

The Treating Neurologist will perform a neurological and physical examination and safety assessment. The Treating Neurologist or designee will document in the eCRF the following:

- Time and date of neurological and physical examination
- Clinical findings of neurological and physical examination
- Review of previously documented concomitant medications and medical history
- Safety assessment, including vital signs, CBC, B-cell count, lymphocyte counts, fibrinogen, quantitative immunoglobulin

Subjects with suspected clinical relapses reported to the Treating Neurologist or designee will be referred to the blinded Examining Neurologist who will use Neurostatus to assess the EDSS independently of the Treating Neurologist.

The Examining Neurologist or designee will document in the eCRF the following:

- Date and time of assessment
- EDSS score
- FS Scores

In addition, subjects may not begin IV methylprednisolone (IVMP) treatment of a relapse until the Examining Neurologist has completed his/her examination.

Treatment of relapses may proceed at the discretion of the Treating Neurologist only after the Examining Neurologist has completed his/her exam. The Treating Neurologist will not know the results of the EDSS assessment. When making determination to treat a potential acute relapse the Treating Neurologist can use IVMP (1.0 g/day for at least 3 days and can be extended to 5 days) and will not affect the subject eligibility to continue in the study.

The subject must re-consent at the time of each IRAP-confirmed or Treating Neurologist medically confirmed relapse to continue.

The findings from either the Treating Neurologist and Examining Neurologist will not be shared. The Examining Neurologist must be blinded to the Treating Neurologist's assessment and vice versa.

Following the completion of assessments by the Treating and Examining Neurologists these results will be sent independently to the IRAP.

3. Confirmation of Relapse by IRAP

All assessments entered into the eCRF from both the Treating Neurologist and the blinded Examining Neurologist, will be sent to an Independent Relapse Adjudication Panel (IRAP). IRAP adjudicates each case based on all available data provided for that case and members are not permitted to contact the site or the sponsor for additional information. The IRAP will, in turn, make the final determination of whether the neurological events meet the criteria for a protocol-defined relapse.

Each episode of relapse must be confirmed by the IRAP, based on the neurological assessments performed by the Treating and/or Examining Neurologist independently by documenting either of the following:

- ≥ 2 points increase on one of the appropriate FS or 1 point on two or more of the appropriate FS. The change must affect the selected FS (i.e., pyramidal, ambulation, cerebellar, brainstem, sensory or visual). Note, the change in FS scores should correspond to the patient's symptoms (e.g., patient reported change in visual acuity should correspond to a change in the vision FS score). Episodic spasm, sexual dysfunction, fatigue, mood change or bladder or bowel urgency or incontinence will not suffice to establish a relapse;
- An increase of ≥ 0.5 points in the EDSS score (unless EDSS score = 0, then an increase of at least 1.0 points is required) from the previous clinically stable assessment.

MS relapses are defined as a new or worsening neurological symptoms lasting ≥ 24 hours with the absence of fever, injury, infection or adverse reactions to medications and accompanied by new neurological findings upon examination by the Examining Neurologist. The symptoms are attributed to MS and are preceded by 30 days of stability or improvement in neurological state. The change in EDSS score as assessed by the Examining Neurologist is ≥ 0.5 increase or ≥ 2 points increase on one of the appropriate FS or 1 point on two or more of the appropriate FS. The change must affect the selected FS (i.e., pyramidal, ambulation, cerebellar, brainstem, sensory or visual). Note, the change in FS scale scores should correspond to the patient's symptoms (e.g., patient reported change in visual acuity should correspond to a change in the vision FS score). Episodic spasm, sexual dysfunction, fatigue, mood change or bladder or bowel urgency or incontinence will not suffice to establish a relapse. Please note: sexual dysfunction and fatigue will not be scored. If the symptoms occur less than 30 days following the onset of a protocol defined relapse, it should be considered part of the same relapse and would not be treated with IVMP within the protocol. New or recurrent neurologic symptoms that evolve gradually over months should be considered disability progression, not an acute relapse and should not be treated with steroids.

The suspected relapse must be reviewed and confirmed by the IRAP; Appendix D. The IRAP will then notify the CRO and Treating Neurologist of the results of its review.

Treating Neurologist or designee will enter into the eCRF whether the neurological symptoms identified were a result of an IRAP-confirmed relapse.

IRAP-confirmed relapses are the sole confirmation of a protocol-defined relapse. However, for instances where IRAP-confirmed relapses may not be feasible, provisions are provided within Section 4.4.2 (Treating Neurologist medically confirmed relapse).

The subject must re-consent at the time of each IRAP-confirmed or Treating Neurologist medically confirmed relapse to continue.

Signing the informed consent form for re-consent (if the subject has a confirmed relapse), to proceed with the study at the next scheduled office visit should be within 6 weeks after first reporting of relapse.

